2.8.2. Pharmacokinetic / Pharmacodynamic Evaluations

Since Insulin is present in the subjects regardless of treatment, standard PK derivations do not apply.

The PK/PD measurements are taken pre-treatment (Day 3) and at end of treatment (Day 8). On Day 3, all subjects received Placebo, so these measurements will be used as the within subject control.

Time matched changes between Day 8 and Day 3 will be derived for the PK and PD parameters for each subject.

The following time intervals will be summarized: 0 to 60 minutes, 60 to 120 minutes, 120 to 180 minutes, 180 to 240 minutes, 240 to 300 minutes, 120 to 300 minutes and 180 to 300 minutes. Please note that the 0 to 60 minute interval will not be summarized, since it is believed that the study drug takes 60 minutes to metabolize.

The following parameters will be derived for Insulin C-Peptide for each subject:

- Positive Area (Area above 0),
- Negative Area (Area below 0),
- Absolute Area (Positive Area + the absolute value of the Negative Area),
- Maximum Difference,
- Time of Maximum Difference,
- Positive Area / hr (for the 120 to 300 minutes and 180 to 300 minutes intervals only),
- Negative Area / hr (for the 120 to 300 minutes and 180 to 300 minutes intervals only), and
- Absolute Area / hr (for the 120 to 300 minutes and 180 to 300 minutes intervals only).

The Positive Areas, Negative Areas and Absolute Areas will be compared using a one-way analysis of variance (ANOVA) with Fisher's LSD being used for pairwise treatment group comparisons.

The maximum difference and time of maximum difference will be compared in a pairwise fashion using the Wilcoxon Rank Sum test.

The PK/PD analysis will be conducted using model-independent methods and will be based on plasma concentrations of insulin and C-peptide. Individual plasma concentrations of insulin and C-peptide will be listed for each subject and sampling time and summarized descriptively using the arithmetic mean, SD, CV (%), median, minimum and maximum. Individual plasma concentration-time profiles of insulin and C-peptide will be plotted on both a linear and a semi-logarithmic scale. Mean values will also be presented graphically.

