- ⁶A standardized breakfast will be provided on Day 1. Beginning with dinner on Day 2 and ending with breakfast on Day 10, breakfast and lunch will be provided no sooner than 45 minutes after corresponding treatment doses. Dinner will be provided at approximately 7pm (±60 minutes). Standardized snacks will be provided between breakfast and lunch, between lunch and dinner, and between dinner and bedtime.
- ⁷Blood samples (scheduled per randomization scheme) for insulin and C-peptide will be drawn pre-dose and every 30 minutes (± 5 minutes) postdose until 5 hours has elapsed.
- ⁸Randomization will occur on the morning of Period 1/Day 4. Crossover will occur on the morning of Period 2/Day 4 and then again on the morning of Period 3/Day 4.
- ⁹Subjects will receive their assigned randomized treatment from the morning of Day 4 through the evening of Day 8. Doses will be administered at approximately 7am (±60 minutes), 1pm (±60 minutes), and 10pm (±60 minutes).

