6.5 Pharmacokinetic/Pharmacodynamic Assessments

Blood samples for PK/PD analysis of absorbed insulin based on C-peptide correction of total insulin levels will be collected during Visit 2, Periods 1, 2, and 3, on Day 3 and Day 8. An indwelling venous catheter may be inserted for the collection of blood samples if deemed necessary. One 4.5 mL sample of total whole blood will be collected for each blood draw.

On Day 3, blood samples will be collected at the following nominal time points relative to the scheduled (per randomization scheme) dose of placebo: predose (45 to 5 mins prior to dosing) and every 30 minutes (\pm 5 minutes) postdose until 5 hours has elapsed. On Day 8, blood samples will be collected at the following nominal time points relative to the scheduled (per randomization scheme) dose of study treatment (active or placebo): predose (45 to 5 mins prior to dosing) and every 30 minutes (\pm 5 minutes) postdose until 5 hours has elapsed. The total volume collected from each subject for PK/PD samples will be approximately 99 mL per treatment Period, for a total of 297 mL during the entire study. Actual blood sampling times must be recorded in the source and eCRF.

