4.1. Post-text Table of Contents

The following post-text tables will be generated.

Table Number	Table title
14.1.1.1	Summary of Subject Screening Disposition (All Subjects)
14.1.1.2	Summary of Subject Disposition (Safety Population)
14.1.1.3	Summary of Subject Disposition (ITT Population)
14.1.2.1	Summary of Demographics and Baseline Characteristics (Safety Population)
14.1.2.2	Summary of Demographics and Baseline Characteristics (ITT Population)
14.1.3	Summary of Medical History / Surgical History / Procedures (Safety Population)
14.1.4.1	Summary of Prior Medications (Safety Population)
14.1.4.2	Summary of Concomitant Medications (Safety Population)
14.1.5.	Summary of Study Medication Usage (Safety Population)
14.2.1.1	Summary of Pre-treatment (day 3) to end of Treatment (day 8) Continuous Glucose Monitoring Mean 24-hour Glucose – (ITT Population)
14.2.2.1	Summary of Pre-treatment (day 3) to end of Treatment (day 8) Continuous Glucose Monitoring Mean Daytime Glucose – (ITT Population)
14.2.2.2	Summary of Pre-treatment (day 3) to end of Treatment (day 8) Continuous Glucose Monitoring Mean Nighttime Glucose – (ITT Population)

Table Number	Table title
14.2.3.1	Summary of Pre-treatment (day 3) to Post Treatment Washout (day 9) Continuous Glucose Monitoring Mean 24-hour Glucose – (ITT Population)
14.2.4.1	Summary of Post-Prandial (Breakfast, Lunch, and Dinner) Glucose Measurements – (ITT Population)
14.2.5.1	Insulin Levels by Time Point (ITT Population)
14.2.5.2	Insulin Parameters by Time Intervals (ITT Population)
14.2.6.1	C-Peptide Levels by Time Point (ITT Population)
14.2.6.2	C-Peptide Parameters by Time Intervals (ITT Population)
14.3.1.1	Adverse Events Overall Summary (Safety Population)
14.3.1.2	Summary of Treatment Emergent Adverse Events by System Organ Class, and Preferred Term (Safety Population)
14.3.1.3	Summary of Treatment Emergent Adverse Events Leading to Discontinuation of Study (Safety Population)
14.3.1.4	Summary of Serious Treatment Emergent Adverse Events (Safety Population)
14.3.1.5	Summary of Treatment Emergent Adverse Events by System Organ Class, Preferred Term, and Severity (Safety Population)
14.3.2	Summary of Laboratory Values (Safety Population)
14.3.3	Summary of Vital Signs (Safety Population)
14.3.4	Summary of Hypoglycemic Events (Safety Population)
14.3.5	Summary of Physical Examination Findings (Safety Population)

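### No PK/PD window spans the full 60 to 300 minutes after assumed onset, so in the three-draw windows the maximum difference and its time are mostly set by the window edges

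*SAP*

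**What the plan says.** Protocol 6.5 sets insulin and C-peptide sampling on Day 3 and Day 8 at "predose (45 to 5 mins prior to dosing) and every 30 minutes" after dosing. The Schedule of Events (Protocol 3.6) says the same: samples are "drawn pre-dose and every 30 minutes (± 5 minutes) postdose until 5 hours has elapsed".

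SAP 2.8.2 works with time-matched Day 8 minus Day 3 differences. It lists seven windows to be summarised: 0 to 60, 60 to 120 and 120 to 180 minutes, followed by "180 to 240 minutes, 240 to 300 minutes, 120 to 300 minutes and 180 to 300 minutes". The next sentence, quoted here without its last word, removes the first of these: "Please note that the 0 to 60 minute interval will not be summarized, since it is believed that the study drug takes 60 minutes to".

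The parameters follow: positive, negative and absolute areas, Maximum Difference, Time of Maximum Difference, and areas per hour. Only the per-hour areas are limited to named windows (120 to 300 and 180 to 300). The areas are compared by one-way ANOVA with Fisher's LSD. For the peak, "The maximum difference and time of maximum difference will be compared in a pairwise fashion using the Wilcoxon Rank Sum test".

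SAP 4.1 has one parameter table per analyte. The insulin one (14.2.5.2) is titled "Insulin Parameters by Time Intervals (ITT Population"), and the C-peptide one (14.2.6.2) matches it. SAP 2.10 plans no further analyses.

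**The concern.** The SAP places onset at 60 minutes and sampling runs to 300, so 60 to 300 minutes is the sampled post-onset profile. No listed window covers it. The two long windows start at 120 and 180 minutes and leave out the first post-onset hour.

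This matters most for the maximum and its time. An hourly window holds three draws, and two of them are edges. The edges at 120, 180 and 240 minutes are each shared by two hourly windows. When the true peak lies outside a window, the largest value inside tends to sit at the edge nearest the peak, and its time reflects where the window was cut. A rank-sum test on that time says little about when the drug acts.

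Two secondary objectives, on insulin PK and C-peptide PD, depend on this section. As written, they get no single comparison of peak, time to peak or total area over the post-onset profile. Separately, SAP 2.8.2 lists 0 to 60 minutes as summarised and in the next sentence says it is not.

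**Working it through.** **1. Draws per profile.** Predose plus one every 30 minutes to 300 gives 1 + 300/30 = 11 draws. Protocol 6.5 allows a check: "One 4.5 mL sample of total whole blood will be collected for each blood draw", with a stated volume of "approximately 99 mL per treatment Period, for a total of 297 mL during the entire study". 11 draws × 2 days × 4.5 mL = 99 mL per period, and × 3 periods = 297 mL. Both figures reproduce exactly.

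**2. Draws per window and edge share under pure noise.** Windows are counted with both end points, as trapezoidal areas require. If the n differences in a window are exchangeable, the maximum is equally likely at each draw, so the share on an edge is 2/n. This needs no effect size or variance.

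| Window (min) | Draws n | Edge share 2/n |
|---|---|---|
| 60–120, 120–180, 180–240, 240–300 | 3 each | 67% |
| 180–300 | 5 | 40% |
| 120–300 | 7 | 29% |
| 60–300 (not planned) | 9 | 22% |

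The mean over the six planned windows is (4 × 0.667 + 0.400 + 0.286)/6 = 56%.

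**3. No noise, single peak.** Take a true peak at 150 minutes. The window maxima fall at 120 (60–120), 150 (120–180), 180 (180–240), 240 (240–300), 150 (120–300) and 180 (180–300). Four of the six are edges. Moving the peak over every draw from 60 to 300 minutes puts the maximum on an edge in 3 or 4 of the four hourly windows, and in 3 to 6 of all six.

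**4. Signal plus noise (assumed, since the documents give no effect shape or variance).**
- *Peak time uniform on 60–300, peak height 0 to 3 SD, correlation 0 to 0.8 between adjacent draws.* Edge share is 66–82% in the hourly windows, 39–54% in 180–300, 27–39% in 120–300 and 14–32% over 60–300.
- *Smooth effect (width 45 minutes), subject peak times around 150 (SD 30) minutes, noise SD 30% of peak height.* Edge share is 62–76% in the hourly windows, 67% in 180–300, 30% in 120–300 and about 2% over 60–300.
- *Same shape, mean peak 130 against 170 minutes, 20 per regimen, rank-sum test at 5%.* Power is roughly 87% over 60–300, 75% over 120–300, 67–70% in 120–180 and 4–20% in the other four windows.

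**5. Areas.** 60–120 and 120–300 meet at 120 with no gap, so for positive, negative and absolute area alike, area(60–300) = area(60–120) + area(120–300). The SAP neither forms nor tests this sum. Whether the single interval is more sensitive depends on the peak time. With signal-to-noise = w′μ/√(w′Cw), where w is the trapezoid weights, μ the effect (width 45 minutes) and C the noise correlation (0.3 to 0.8 between adjacent draws), the ratio of 120–300 to 60–300 is:

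| Effect | Ratio |
|---|---|
| Peak at 105 min | 0.53–0.57 |
| Peak at 150 min | 0.90–0.96 |
| Peak at 180 min | 1.07–1.14 |
| Peak at 210 min | 1.15–1.23 |
| Constant from 60 min | 0.88–0.95 |

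For the peak at 105 minutes, the planned 60–120 window has 1.36–1.84 times the signal-to-noise of 60–300.

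**The case against.** The strongest reply is that no sentence in SAP 2.8.2 takes the maximum per window. The parameters are said to be derived for each subject, and the table shells that would settle the matter are in a separate file. This stands as a limit on the claim. Still, the order of the lists, the interval restriction placed on the per-hour areas alone, and the table titles all point to per-window derivation. If one maximum per profile was meant, the SAP names no window for it and does not say whether the first hour counts. Either reading needs the same repair.

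A reader might infer that all the planned tests on time of maximum compare window edges. The documents do not support that: 120–300 is a planned window with seven draws, and its maximum is usually interior.

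A reader might also infer that total exposure goes unexamined, or that an early effect is lost. Neither follows. 60–120 and 120–300 together cover the post-onset profile, both sets of areas are tested, and for an early peak 60–120 is the more sensitive interval. What is missing is a comparison of the total as one quantity.

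Finally, the analysis is secondary, the study claims no power, and full profiles are tabulated by time point and plotted. That limits the weight of the point. It does not make the planned rank-sum tests easier to interpret.

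**Conclusion.** The point holds for the maximum and its time. Four of the six reported windows hold three draws, and there the maximum sits on an edge 67% of the time under pure noise. The 120–300 window is less affected (29%) but omits the first post-onset hour. Time-of-maximum tests in the three-draw windows do not measure time to peak, and no planned window gives a maximum over the whole post-onset profile.

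For the areas, the gap is only that the post-onset total is not compared as one quantity. The stronger inference, that 60–300 should displace the shorter windows as the main area interval, is not supported: step 5 shows the better interval changes with a peak time the documents do not give. Nor can 0–60 safely serve as a no-effect control. By Day 8 subjects have had four days of assigned treatment, and breakfast or lunch may start 45 minutes after the dose.

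The draw counts, the missing window and the pure-noise shares follow from the documents, given closed windows and, for the shares, exchangeable differences. The power and signal-to-noise figures are illustrative. This is a low-cost improvement to a secondary analysis and does not touch the primary CGM comparison.

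**What to change.** In SAP 2.8.2 and Tables 14.2.5.2 and 14.2.6.2:

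- Derive and test Maximum Difference and Time of Maximum Difference once per profile, over 60 to 300 minutes, and say so.
- Add 60 to 300 minutes as a further interval for the positive, negative and absolute areas.
- Keep the planned area analyses in the shorter windows.
- Delete 0 to 60 minutes from the list of summarised intervals, so that it agrees with the sentence that follows it.

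The cost is SAP wording and two table shells. Samples and blood volume do not change. The extra interval adds 3 areas × 2 analytes = 6 ANOVAs. On the per-window reading, the sets of pairwise rank-sum comparisons fall from 6 windows × 2 measures × 2 analytes = 24 to 2 × 2 = 4.

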1.3.2 Secondary Objectives

Secondary objectives are:

- To compare pre-treatment (Day 3) to end of treatment (Day 8) mean daytime CGM glucose for single and multiple doses of ORMD-0801 vs placebo.
- To compare pre-treatment (Day 3) to end of treatment (Day 8) mean nighttime CGM glucose for single and multiple doses of ORMD-0801 vs placebo.
- To compare pre-treatment (Day 3) to post-treatment washout (Day 9) 24-hour CGM glucose for single and multiple doses of ORMD-0801 vs placebo.
- To compare post-prandial glucose measurements for single and multiple doses of ORMD-0801 vs placebo.

- To compare pre-treatment (Day 3) to end of treatment (Day 8) insulin pharmacokinetics (PK) for single and multiple doses of ORMD-0801 vs placebo.
- To compare pre-treatment (Day 3) to end of treatment (Day 8) C-peptide pharmacodynamics (PD) for single and multiple doses of ORMD-0801 vs placebo.
- To compare defined events of hypoglycemia for single and multiple doses of ORMD-0801 vs placebo.

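### The insulin and C-peptide comparison tests positive, negative and absolute areas but no net signed area, so no planned area test cleanly measures the mean Day 3 to Day 8 change

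*SAP*

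**What the plan says.** The secondary objectives compare Day 3 with Day 8 for "insulin pharmacokinetics (PK) for single and multiple doses of ORMD-0801 vs placebo", with a matching objective for C-peptide (SAP 1.3.2). SAP 2.8.2 starts from a signed quantity: "Time matched changes between Day 8 and Day 3 will be derived for the PK and PD parameters for each subject".

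That curve is reduced, per interval, to three areas: "Positive Area (Area above 0", "Negative Area (Area below 0" and "Absolute Area (Positive Area + the absolute value of the Negative Area". The comparison is then: "The Positive Areas, Negative Areas and Absolute Areas will be compared using a one-way analysis of variance (ANOVA) with Fisher's LSD" for the pairwise contrasts. Two further parameters are tested: "The maximum difference and time of maximum difference will be compared in a pairwise fashion using the Wilcoxon Rank Sum test". The SAP does not say whether the maximum difference keeps its sign.

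Neither SAP 2.8.2 nor Protocol 8.2 derives or tests a net signed area or a mean change over an interval, and SAP 2.10 plans no other analyses. For glucose, by contrast, SAP 2.8.1 does test a signed mean change.

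**The concern.** The question for insulin and C-peptide is whether the level moved between Day 3 and Day 8, and which way. Direction matters: the Protocol introduction says earlier studies of the product showed reduced C-peptide.

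The variable that answers this is the net signed area, or equivalently that area divided by the interval length. Splitting the curve at zero changes what is tested. Even with no mean change, random fluctuation gives a positive area, a negative area and an absolute area all different from zero, and each grows in proportion to the SD of the difference. A group with more variable differences therefore has larger areas without any treatment shift. Absolute Area also counts a rise and a fall alike.

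At stake is how the PK/PD p-values are read. A significant area could reflect a shift or a difference in variability, and a shift could be reported as absent on Absolute Area.

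**Working it through.** The documents give no power, SD or effect size for PK/PD, so there is no figure of the plan's to reproduce.

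**Inputs from the documents.** Samples every 30 minutes to 5 hours (Protocol 6.5), so the 120 to 300 minute interval has 7 points over 3 hours. One-way ANOVA with Fisher's LSD (SAP 2.8.2). About 30 subjects, each on placebo plus two of three regimens (Protocol 5.2).

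**Assumptions.** Balanced allocation: 30 placebo and 20 records per regimen, 90 in all, error df 90 - 4 = 86. Two-sided 5%, critical t 1.988 (no PK/PD alpha is stated). AR(1) 0.5 between time points. Records independent, as the one-way ANOVA treats them. Unit: the SD of one time-point difference. Areas are trapezoids with exact zero crossings.

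**1. Equal noise, all active regimens shifted by +0.5 SD.** Simulated mean (SD) of each area, in SD-hours:

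| Area | No shift | +0.5 SD | Difference |
|---|---|---|---|
| Net | 0.00 (1.845) | 1.50 (1.845) | 1.50 |
| Positive | 1.094 (1.027) | 2.005 (1.368) | 0.911 |
| Negative | -1.090 (1.021) | -0.501 (0.664) | 0.589 |
| Absolute | 2.184 (0.890) | 2.506 (1.106) | 0.322 |

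Check: 0.5 SD x 3 h = 1.5, and 2.005 - 0.501 = 1.504.

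SE = pooled SD x sqrt(1/20 + 1/30) = pooled SD x 0.2887, with pooled SD = sqrt((29 x placebo variance + 57 x active variance)/86). Power is roughly Phi(difference/SE - 1.988).

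- Net: 1.50/(1.845 x 0.2887) = 2.82, power 80%.
- Positive: pooled SD 1.263; 0.911/0.365 = 2.50, power 70%.
- Negative: pooled SD 0.802; 0.589/0.232 = 2.54, power 71%.
- Absolute: pooled SD 1.038; 0.322/0.300 = 1.07, power 18%.

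Simulation of the same setting (4,000 runs) gave 79%, 69%, 72% and 16%. Over correlation settings from strongest to none, the ranges are net 51-99%, positive 41-98%, negative 42-97% and absolute 11-42%.

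**2. No shift, active-group noise 1.5 times larger.** Every area scales by 1.5.

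- Absolute: 3.276 - 2.184 = 1.092; pooled SD sqrt((29 x 0.890² + 57 x 1.335²)/86) = 1.203; 1.092/0.347 = 3.14, rejection about 88%.
- Positive: 1.641 - 1.094 = 0.547; pooled SD 1.389; 0.547/0.401 = 1.36, rejection about 27%.
- Net: the expected difference stays 0.

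Simulation gave absolute 89%, positive and negative 25%, net 4%. Allowing the noisier group to be either the active groups or placebo, the ranges are:

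| Noise ratio | Absolute | Positive or Negative | Net |
|---|---|---|---|
| 1.25 | 42-50% | 11-13% | 4-7% |
| 1.5 | 88-94% | 25-34% | 4-7% |

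If only the compared regimen is noisier, the pooled error is too small for that contrast. Net area then also drifts above 5%, but far less than the planned areas.

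**3. Could variability differ between groups?** Protocol 5.2 gives each subject one morning, one afternoon and one evening draw period, with active draws only after an active dose. So:

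- qd + bid: qd evening, bid morning, placebo afternoon.
- qd + tid: qd evening, placebo morning or afternoon.
- bid + tid: four permitted layouts, with placebo afternoon in two, morning in one and evening in one.

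With 10 subjects per pair and permitted layouts equally likely, placebo draws are 10 + 5 + 5 = 20 afternoon, 5 + 2.5 = 7.5 morning and 2.5 evening, out of 30. All 20 qd draws are in the evening. The afternoon window contains lunch; the evening window (10pm to 3am) contains no main meal.

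**The case against.** A reader might infer that all the planned tests respond to noise rather than direction, so that the plan would miss a real shift. The documents do not support that. Positive and Negative Area are tested separately, move in opposite ways under a shift, and lose only about 10 points of power to net area under equal noise. A shift that net area detects would usually show in one of them. This defence stands for equal noise. With unequal noise it weakens, because the same p-value can come from variability, and the noise effect can offset a true shift in the area that should show it.

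A reader might also infer that unequal variability is built into the design. It is not established. The change is time-matched within subject, meals are standardized on both days, and the draw allocation sits in a separate randomization plan (SAP 2.12). The two-thirds afternoon figure for placebo needs balance and equally likely layouts, and the noise ratios come from neither document. Time-matching removes the slot's mean but not its variance, so the possibility remains.

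Direction is already visible in the level tables and mean plots (Tables 14.2.5.1 and 14.2.6.1 and the mean figures), and per-subject areas are listed. Net area, its SD and a test can therefore be built afterwards from the listings. That is true, but the comparison would then not be prespecified. The maximum difference is a single-point summary of unstated sign and does not replace it.

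The strongest point concerns the remedy: net area cancels when a profile rises and then falls. For a mean difference running from +1 to -1 SD across 120 to 300 minutes, net area has 5-6% power and Absolute Area 32%. This stands, and it argues against dropping the existing areas.

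**Conclusion.** The gap is real but limited. A signed change is derived and its mean is never tested. Absolute Area cannot show direction and has little power for modest shifts (about 18% at 0.5 SD, against about 80% for net area), although at a 1 SD shift it reaches 56-100% across the correlation settings. Positive and Negative Area are usable directional tests whose results are confounded with variability if the groups differ in noise.

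The figures rest on the assumed allocation, correlation, alpha and constant shift, and the inflation figures on illustrative noise ratios. They show how each test behaves; they do not predict this trial's error rates. The endpoints are secondary, the study is declared not powered for significance, and the primary glucose result is unaffected. This is an inexpensive improvement to interpretation.

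**What to change.** In SAP 2.8.2, derive the net signed area (Positive Area plus the signed Negative Area) per subject, interval and analyte, and name it as the main between-treatment PK/PD comparison. Dividing it by the interval length in hours gives the mean time-matched change. Keep the positive, negative and absolute areas as supporting analyses, and state that Absolute Area is not evidence of direction. Add the variable to Tables 14.2.5.2 and 14.2.6.2 and to the matching parameter listings.

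The cost is one derived variable, one more test per interval and analyte, and a few lines of SAP text; no new data are needed. The downside is that net area can cancel when a profile rises and then falls within an interval, which is why the existing areas stay.
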